The primary estimand is defined as the treatment difference between subjects randomised to faster aspart and NovoRapid[®] both in combination with insulin degludec with or without metformin, in adults with T2DM not optimally controlled with a basal-bolus regimen assessed by change from baseline in HbA_{1c} 16 weeks after randomisation for all randomised subjects regardless of treatment discontinuation or use of ancillary treatment.

The primary estimand assesses the expected benefit a future population with T2DM can achieve if prescribed to faster aspart as compared to NovoRapid[®]. By not putting any restrictions on the treatment adherence, this estimand aims at a difference as close as possible to the one that can be expected in real-world clinical practice, provided that the treatment adherence and use of ancillary treatment reflects clinical practice. Thereby the primary estimand provides a treatment difference for clinicians concerning the glycaemic effect of faster aspart compared to NovoRapid[®] in the day to day life in subjects with T2DM in an adult population.

Secondary estimand

A secondary estimand is defined as the treatment difference in change from baseline in HbA_{1c} 16 weeks after randomisation between treatment with faster aspart and treatment with NovoRapid both in combination with insulin degludec with or without metformin in adult subjects with T2DM not optimally controlled with a basal-bolus regimen if all subjects had adhered to randomised treatment and did not receive ancillary treatment.

The condition 'adhered to randomised treatment and did not receive ancillary treatment' should be interpreted as the exclusion of information collected after initiation of antidiabetic treatment that can mask or exaggerate the effect of the initially randomised treatment. Only data collected prior to

discontinuation of trial product or initiation of ancillary treatment is used to draw inference. This avoids confounding effects of ancillary treatment.

The two estimands will be repeated for the confirmatory endpoints

- Change from baseline in 1-hour PPG increment (meal test) 16 weeks after randomisation
- Change from baseline in 1,5-anhydroglucitol 16 weeks after randomisation

Visit reallocation

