2.4 Secondary endpoints

2.4.1 Confirmatory secondary endpoints

If the effect of treatment with faster aspart can be confirmed in the primary analysis, the trial also aims to confirm effect of treatment with faster aspart for a number of secondary confirmatory endpoints using a hierarchical (fixed sequence) testing procedure as described in section 2 (General consideration). This is based on a priority ordering of the null-hypotheses, and testing them in this order using the two-sided 95% confidence interval approach until an insignificant result appears. The effect is that rejection of the null hypothesis will only be confirmed for endpoints where all previous null-hypotheses have been rejected in favour of faster aspart.

The confirmatory secondary endpoints are:

- Change from baseline in 1-hour PPG increment 16 weeks after randomisation (meal test)
- Change from baseline in 1,5-anhydroglucitol 16 weeks after randomisation

The steps in the hierarchical testing procedure are as follows:

- Step 1 (Primary analysis): HbA_{1c} non-inferiority of faster aspart versus NovoRapid[®]
- Step 2: 1-hour PPG increment (meal test) superiority of faster aspart versus NovoRapid®
- **Step 3:** HbA_{1c} superiority of faster aspart versus NovoRapid[®]
- Step 4: 1,5-anhydroglucitol superiority of faster aspart versus NovoRapid®

The primary estimand for the primary endpoint will be repeated for the confirmatory secondary endpoints, change from baseline in 1-hour PPG increment (meal test) and change from baseline in 1,5-anhydroglucitol 16 weeks after randomisation. The analyses related to these estimands are defined below and will be used for the decisions to continue or not, throughout the hierarchical testing procedure. These analyses will be based on the FAS and use the in-trial observation period.

Statistical Analysis Plan		Date:	12 February 2019	Novo Nordisk
Trial ID: NN1218-4113	CONFIDENTIAL	Version:	2.0	
UTN: U1111-1180-0636	CONFIDENTIAL	Status:	Final	
EudraCT No.: 2016-000878-38		Page:	16 of 29	

As sensitivity analysis the secondary analysis 4) will also be repeated for the confirmatory secondary endpoints. The analyses will be based on the FAS and using the on-treatment observation period.

Change from baseline in 1-hour PPG increment 16 weeks after randomisation (meal test) (step 2)

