As the second step of the hierarchical testing procedure change from baseline in 1-hour PPG increment (meal test) 16 weeks after randomisation will be tested for superiority of faster aspart compared to Novo Rapid[®].

The 1-hour PPG increment will be analysed based on the laboratory measured values in the meal test, and is derived as the 1-hour PPG measurement minus the pre-prandial PG measurement.

The 1-hour PPG increment endpoint will be analysed using the FAS and the in-trial observation period based on a multiple imputation technique where the change from baseline in 1-hour PPG increment at week 16 for subjects with missing value are imputed based on data from subjects in the NovoRapid® arm with non-missing values at week 16. Multiple copies (100 copies) of the full dataset will be generated by imputing missing values based on estimated parameters as follows:

- An analysis of variance model with region and metformin use at baseline (Yes/No) as factors and baseline 1-hour PPG increment as covariate is fitted to the change from baseline in 1-hour PPG increment at week 16 for the NovoRapid® group only. The estimated parameters, and their variances, from this model are used to impute missing values using stochastic simulation at week 16 for subjects in both treatment groups in order to generate 100 complete datasets.
- For each of the complete data sets, the change from baseline to week 16 is analysed using an analysis of variance model with treatment, region and metformin use at baseline (Yes/No) as factors, and baseline 1-hour PPG increment as covariate.
- The estimates and standard deviations for the 100 data sets are pooled to one estimate and associated standard deviation using Rubin's formula. From this, the pooled estimate and 95% confidence interval for the treatment difference are calculated.

The superiority will be assessed by comparing the upper limit of the 95% CI to 0. If the upper 95% CI is below 0 then superiority will be confirmed.

Change from baseline in HbA_{1c} 16 weeks after randomisation (step 3)

Step 3 in the hierarchical testing procedure is to confirm superiority of change from baseline HbA_{1c} 16 weeks after randomisation of the effect of treatment with faster aspart compared to NovoRapid[®]. Superiority will be addressed based on the same 95% CI that was used for addressing the primary

Statistical Analysis Plan		Date:	12 February 2019	Novo Nordisk
Trial ID: NN1218-4113	CONFIDENTIAL	Version:	2.0	

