2.4.2 Supportive secondary endpoints

2.4.2.1 Efficacy endpoints

All endpoints except insulin dose in this section will be assessed using the FAS and the in-trial observation period and repeated using the on-treatment observation period. Insulin dose will be presented using the safety analysis set and will therefore only use the on-treatment observation period.

Change from baseline in FPG 16 weeks after randomisation

Change from baseline in FPG 16 weeks after randomisation will be analysed based on all planned post baseline measurements until or at 16 weeks after randomisation using a model similar to 1) except with baseline FPG as covariate.

If a subject achieves HbA_{1c} target 16 weeks after randomisation

$HbA_{1c} < 7.0\%$

A dichotomous (responder/non-responder) endpoint will be defined based on whether a subject has met the HbA_{1c} target ($HbA_{1c} < 7.0\%$) 16 weeks after randomisation.

This responder endpoint will be analysed based on a logistic regression model using treatment, region and metformin use at baseline (Yes/No) as factors, and baseline HbA_{1c} as covariate. In analysis of the in-trial observation period subjects without an HbA_{1c} measurement at week 16 will be treated as non-responders. In the analysis using the on-treatment observation period subjects who discontinue randomised treatment, initiate ancillary treatment, withdraw from trial, and/or have no HbA_{1c} measurement at week 16 are included as non-responders.

Statistical Analysis Plan Trial ID: NN1218-4113 UTN: U1111-1180-0636 EudraCT No.: 2016-000878-38

CONFIDENTIAL

Date: Version: Status: Page:

12 February 2019 | Novo Nordisk Final 18 of 29

$HbA_{1c} < 7.0$ % without severe hypoglycaemia

A dichotomous (responder/non-responder) endpoint will be defined based on whether a subject has met the HbA_{1c} target (HbA_{1c} <7.0%) 16 weeks after randomisation without treatment emergent severe hypoglycaemic episodes.

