This responder endpoint will be analysed based on a logistic regression model using treatment, region and metformin use at baseline (Yes/No) as factors and baseline HbA_{1c} as covariate. In the analysis of the in-trial observation period subjects without an HbA_{1c} measurement at week 16 will be treated as non-responders. In the analysis using the on-treatment observation period subjects who discontinue randomised treatment, initiate ancillary treatment, withdraw form trial, and/or have no HbA_{1c} measurement at week 16 will be included as non-responders.

Change from baseline in 30- minutes, 1- hour, 2- hour, 3- hour and 4- hour PPG and 30minutes, 2- hour, 3- hour and 4- hour PPG increment 16 weeks after randomisation (meal test)

Laboratory measured PG from the meal test will be analysed for 30 minutes, 1-hour, 2-hours, 3hours and 4-hours PPG separately. The corresponding PPG increments will be derived separately using each PPG measurement minus the pre-prandial PG measurement.

Change from baseline in PPG and PPG increment 16 weeks after randomisation will be analysed separately using a model similar to the model used in hierarchical testing procedure step 2 for 1hour PPG increment 16 weeks after randomisation (meal test) except with the corresponding baseline value as covariate.

Change from baseline in endpoints derived from the 7-9-7-point SMPG profile 16 weeks after randomisation

In general, analyses will be based on the entire 7-9-7-point SMPG profile except for the analyses of nocturnal endpoints where information in the 9-point SMPG profile will be utilised.

PPG and PPG increments based on the 7-9-7-point SMPG profiles will be derived separately for PG measurements made 1 hour after the meal. In the following section this distinction will be considered implicit and without further explanation.

Pre-prandial PG and PPG will be recorded by the subjects as part of the 7-9-7-point SMPG profile prior to three defined visits. Individual mean mealtime PPG (post-breakfast, post-lunch, post-main evening meal) will be derived from the three profiles. Overall mean PPG will be derived from the individual derived mealtime PPG values.

PPG increment for each meal (breakfast, lunch, main evening meal) will be derived from the 7-9-7point SMPG profile as the difference between PPG values and pre-prandial PG values in each

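### In the on-treatment repeat, the supportive meal-test endpoints are still imputed from NovoRapid, while the 1-hour increment is imputed from the subject's own arm

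*SAP*

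**What the plan says.** SAP 2.4.2.1 states that every supportive efficacy endpoint except insulin dose "will be assessed using the FAS and the in-trial observation period and repeated using the on-treatment observation period". Within that section, change from baseline in meal-test PPG at five time points, and in the increments at 30 minutes and 2, 3 and 4 hours, "will be analysed separately using a model similar to the model used in hierarchical testing procedure step 2". The only departure named is "except with the corresponding baseline value as covariate". No separate imputation rule is given for the on-treatment repeat.

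The step 2 model is in SAP 2.4.1. Missing week-16 changes are "imputed based on data from subjects in the NovoRapid® arm with non-missing values at week 16". The imputation model is fitted to that arm alone and supplies values "for subjects in both treatment groups in order to generate 100 complete datasets".

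The 1-hour increment is a confirmatory endpoint and has its own on-treatment rule, also in SAP 2.4.1: "As sensitivity analysis the secondary analysis 4) will also be repeated for the confirmatory secondary endpoints". In SAP 2.3, analysis 4 is the model of primary analysis 1 applied to on-treatment data, and analysis 1 imputes from the arm to which the subject was randomised.

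Protocol version 4.0, sections 17.4.1 and 17.4.2.1, has the same structure. SAP section 3, which lists changes from the protocol, does not mention the point.

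**The concern.** In SAP 2.3 the on-treatment period carries the secondary estimand, which SAP section 2 defines as the treatment difference "if all subjects had adhered to randomised treatment and did not receive ancillary treatment". The visit-reallocation rule in the same section also chooses between Visit 30A and later values according to the estimand.

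In that window, a faster aspart value can be absent because the subject stopped trial product or began ancillary treatment. If the gap is filled from the NovoRapid model, that subject is assumed to have no faster aspart effect. This is a sensible conservative choice for the in-trial superiority test. It sits awkwardly in an analysis restricted to on-treatment data.

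It also splits one set of measurements. The 1-hour PPG and the 1-hour increment both come from the 60-minute sample. If that sample is missing, the on-treatment analysis draws the first from NovoRapid and the second from the subject's own arm. The on-treatment increment profile then has one time point on one assumption and four on another, and a reader of the tables would not see it.

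**Working it through.** **Which arm supplies the imputations, on-treatment**

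| Endpoint | Rule in the SAP | Source for a missing faster aspart value |
|---|---|---|
| 1-hour increment | 2.4.1, analysis 4 (2.3) | Own arm |
| 30-minute, 2-, 3-, 4-hour increments | 2.4.2.1, step 2 model | NovoRapid |
| 30-minute, 1-, 2-, 3-, 4-hour PPG | 2.4.2.1, step 2 model | NovoRapid |
| FPG, continuous SMPG measures, lipids | 2.4.2.1, model similar to analysis 1 | Own arm |

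Among the continuous supportive endpoints analysed by multiple imputation in 2.4.2.1, the meal-test endpoints are the only ones with a NovoRapid source, and no reason is given for keeping it in the on-treatment repeat.

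**Inputs for the size (SAP 2.1)**

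- Difference 0.6 mmol/L and SD 3.5 mmol/L, both for the 1-hour increment. No differences are given for the supportive time points, so 0.6 serves only as an illustration.
- 536 subjects per arm, two-sided 5%.
- Treatment discontinuation about 10%, of which half is trial discontinuation, so 5%.

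**Reproducing the plan's figure.** The standard error is 3.5 × √(2/536) = 0.214 mmol/L. Two-sided power at 0.6 is 80.1% by the normal approximation and by the noncentral t (0.8013 and 0.8006). The plan states 80.1%.

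**Shrinkage.** Let m be the share of faster aspart subjects with an imputed week-16 value, Δ the difference on treatment, and μ the NovoRapid mean. Assume missingness is unrelated to outcome.

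- Faster aspart arm after NovoRapid imputation: (1 − m)(μ + Δ) + mμ = μ + (1 − m)Δ
- NovoRapid arm: μ
- Estimated difference: (1 − m)Δ

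| m | NovoRapid imputation | Loss | Loss ÷ standard error | Own-arm imputation |
|---|---|---|---|---|
| 5% | 0.6 × 0.95 = 0.57 | 0.03 | 0.03 / 0.214 = 0.14 | 0.60 |
| 10% | 0.6 × 0.90 = 0.54 | 0.06 | 0.06 / 0.214 = 0.28 | 0.60 |

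A simulation agrees. It used 2,000 trials, 536 per arm, 30 imputations pooled by Rubin's rules, values missing completely at random and no covariates. NovoRapid imputation gave 0.566 and 0.539, and own-arm imputation gave 0.596 and 0.598.

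**What m might be.** The 10% is a discontinuation rate, not a rate of missing on-treatment meal tests. Protocol 8.1.9 requires a Visit 30A meal test before trial product is stopped, and 8.1.10 asks sites to encourage one at withdrawal. SAP section 2 moves Visit 30A data to the next visit at which the assessment is planned, which for the meal test is week 16, and uses them for the secondary estimand. This lowers m. Two things raise it:

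- A subject who starts ancillary treatment but stays on trial product has no Visit 30A, and the on-treatment window closes about a week after ancillary treatment starts.
- Tests can be missed because of the fasting, hypoglycaemia and starting-glucose conditions in Protocol 8.3.1.

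**The case against.** **The SAP sets no adherence target for these endpoints.** It extends the two estimands by name only to the confirmatory endpoints. In SAP 2.4.2.1 the on-treatment responder analyses count subjects who stop, start ancillary treatment or withdraw as non-responders, which is not an effect under adherence. This stands. A reader might infer that the repeat breaches a stated estimand, and the documents do not support that. What remains is that SAP 2.3 and the visit-reallocation rule link the on-treatment period to that estimand, and that the FPG, continuous SMPG and lipid repeats are imputed from the subject's own arm.

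**Analysis 4 cannot be carried over unchanged.** It is a sequential model over weeks 4, 8, 12 and 16, while the meal test has one scheduled post-baseline assessment. The SAP does not say how it is adapted, so the step 2 model on on-treatment data is a possible reading, and under it the mismatch disappears. But the analysis of the 1-hour increment under the secondary estimand would then itself assume no faster aspart effect in imputed subjects. The wording that the model is only similar to step 2 also leaves room. On any of these readings the imputation source needs to be stated.

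**The consequence is slight.** These endpoints lie outside the testing hierarchy, this is their second analysis, and the pull is towards no difference, so it favours no claim for faster aspart. Protocol 3.1.3 reports that a 2-hour increment benefit could not be confirmed in an earlier type 2 trial, and shrinking a near-zero effect changes little. Protocol 5.3 does not allow other diabetes treatment to be started, so ancillary use should add little to m. All of this stands and limits the weight of the point.

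**Conclusion.** The point holds as an inconsistency in the specification with a small effect. Taken literally, the on-treatment repeat of nine supportive meal-test endpoints (five PPG, four increments) inherits NovoRapid imputation, while the on-treatment 1-hour increment and the FPG, continuous SMPG and lipid repeats use own-arm imputation. The 1-hour increment is therefore out of line with the other four increments and with 1-hour PPG.

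A reader might go further and conclude that the whole on-treatment glucose curve cannot be read across time. That does not follow, because all five PPG time points share one rule.

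The estimates move towards zero in proportion to the imputed share. The illustrative loss is 0.03 mmol/L at 5% and 0.06 at 10%, at most 0.28 of a standard error over that range. It rests on a 0.60 mmol/L effect borrowed from the 1-hour increment, which is not itself affected, and on missingness unrelated to outcome. The true share is unknown and is probably below 10%. Type I error control, the in-trial analyses and every confirmatory conclusion are unaffected.

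**What to change.** Add to SAP 2.4.2.1, under the meal-test endpoints: *In the on-treatment repeat of the meal-test endpoints, missing week-16 values are imputed from the subject's own randomised arm, in a single-step model, as for the on-treatment analysis of the 1-hour increment (analysis 4).* This also settles how analysis 4 is adapted to an endpoint with one scheduled post-baseline assessment. Keep the reference-based version for the in-trial analysis.

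The cost is one sentence and one change of imputation source in the program. Nothing is lost, because the conservative analysis remains in-trial. If the sponsor prefers NovoRapid imputation in both windows, the on-treatment results should be labelled as reference-based, and the imputation source for the 1-hour increment should be stated beside them.

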8.3.3 Self-measured plasma glucose

At Visit 2, subjects will be provided with a BG meter including ancillaries as well as instructions for use, if needed. The subjects will be instructed in how to use the device.

The subjects should be instructed how to record the results of the SMPG values including a 7-9-7 point profile in the diaries. Data from the diary must be transcribed into the eCRF during or following the contact. If obtained via phone and a discrepancy is later detected, the values in the eCRF must be corrected.

Protocol		Date:	23 February 2018	Novo Nordisk
Trial ID: NN1218-4113	CONFIDENTIAL	Version:	4.0	
UTN: U1111-1180-0636	CONFIDENTIAL	Status:	Final	
EudraCT no.: 2016-000878-38		Page:	45 of 112	

Occasional review by the investigator of the values stored in the memory of the BG-meter and correct reporting of these in the diary is advised in order to ensure adequacy of the data reported in the trial database.

The BG meters use test strips calibrated to plasma values. Therefore, all measurements performed with capillary blood are automatically calibrated to plasma equivalent glucose values, which will be shown on the display.

Only the BG meter provided by Novo Nordisk should be used for the measurements required in the protocol.

4-point self-measured plasma glucose profile

The 4-point SMPG profile will be recorded for insulin titration purposes. Subjects will be instructed to perform 4-point profiles every day from Visit 2 to Visit 30 for titration purposes. The measurements should be performed at the following time points:

- Before breakfast
- Before lunch
- Before main evening meal (dinner)
- At bedtime

For SMPG measurements actual clock time, time point (e.g. before breakfast), date and value should be recorded in the diary.

SMPG values measured before breakfast, lunch, main evening meal, and at bedtime should be performed before any injection of bolus insulin and just before the start of the meal (breakfast, lunch or main evening meal). SMPG values measured before breakfast should be performed in a fasting condition. The 4-point profile is part of the 7- or 9-point profiles which are measured prior to selected site visits.

7-9-7 point self-measured plasma glucose profile

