The 7- and 9-point SMPG profiles will be used for titration purposes and evaluation of the effect of the trial. The subject will be instructed to perform a 7-9-7 point profile on the 3 consecutive days just before selected visits as outlined in the flowchart in section $\underline{2}$. See $\underline{\text{Table 8-2}}$ (7-point profiles indicated as X and the 9-point profile indicated as $\sqrt{ }$).

Protocol Da	Date: 23 February 2018	Novo Nordisk
-------------	------------------------	--------------

 Trial ID: NN1218-4113
 Version: 4.0

 UTN: U1111-1180-0636
 Status: Final Page: 46 of 112

Table 8–2 7-point SMPG profiles with additional 9-point SMPG profile

Time point	Day -3 7-point profile	Day -2 9-point profile	Day -1 7-point profile
Before breakfast	X	1/	√(X) ^a
60 minutes after the start of breakfast	X	1/	X
Before lunch	X	1/	X
60 minutes after the start of lunch	X	1/	X
Before main evening meal	X	1/	X
60 minutes after the start of main evening meal	X	1/	X
At bedtime	X	1/	X
At 4 am		1/	

^aThe last SMPG in the 9-point profile and the first SMPG of the 7-point profile on day-1 are overlapping.

For SMPG measurements actual clock time, time point (e.g. before breakfast), date and value should be recorded in the diary. SMPG values measured before breakfast, lunch and main evening meal and at bedtime should be performed before any insulin injection and just before the start of the meal (breakfast, lunch or main evening meal). SMPG values measured before breakfast should be performed in a fasting condition.

The measurements will be used to evaluate the glucose profile.

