separate profile. The mean of the derived increments will then be calculated separately for each meal. Mean 1 hour PPG increments over all meals will be derived as the mean of all corresponding mean meal increments.

• Change from baseline in mean of the 7-9-7-point SMPG profile

The mean of the 7-9-7-point SMPG profile is defined as the area under the curve profile divided by the measurement time, and is calculated using the linear trapezoidal technique.

Change from baseline in the mean of the 7-9-7-point SMPG profile 16 weeks after randomisation will be analysed based on all planned post baseline measurements until or at 16 weeks after randomisation using a model similar to 1) except with the corresponding baseline value as covariate.

• Change from baseline in PPG and PPG increment (mean, breakfast, lunch and main evening meal)

Change from baseline in PPG and PPG increment endpoints 16 weeks after randomisation for mean over all three meals and the individual meals will be analysed separately based on all planned post baseline measurements until or at 16 weeks after randomisation using a model similar to 1) except with the corresponding baseline value as covariate.

• Fluctuation in 7-9-7-point SMPG profile

The fluctuation in the 7-9-7-point SMPG profile is defined as:

$$\frac{1}{T} \int_{0}^{T} |PG(t) - \overline{PG}| dt$$

where T, PG(t) and \overline{PG} denotes the length of the profile, the PG value at time t and the mean of the profile, respectively. It will be calculated using the linear trapezoidal technique.

Fluctuation in the 7-9-7-point SMPG profile will be logarithmically transformed and analysed based on all planned post baseline measurements until or at 16 weeks after randomisation using a model similar to 1) except with the corresponding log-transformed baseline value as covariate. Estimated treatment means and the estimated treatment differences with corresponding 95% CI will be back-transformed to the original scale, resulting in estimated geometric means, a treatment ratio and a 95% CI for the treatment ratio.

• Change from baseline in nocturnal SMPG measurements

Statistical Analysis Plan		Date:	12 February 2019	Novo Nordisk
Trial ID: NN1218-4113	CONFIDENTIAL	Version:	2.0	
UTN: U1111-1180-0636	CONFIDENTIAL	Status:	Final	
EudraCT No.: 2016-000878-38		Page:	20 of 29	

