Change from baseline in nocturnal SMPG measurements will be assessed by considering the difference between PG values available at bedtime, at 4 AM and the before breakfast value the following day: (4 AM PG value minus at bedtime PG value), (before breakfast PG value minus at bedtime PG value) and (before breakfast PG value minus 4 AM PG value).

Change from baseline in nocturnal SMPG measurements 16 weeks after randomisation will be analysed based on all planned post baseline measurements until or at 16 weeks after randomisation using a model similar to 1) except with the corresponding baseline values as covariate.

If a subject achieves PPG target (based on overall mean of daily PPG measurements in 7-9-7-point SMPG profile) 16 weeks after randomisation:

Overall PPG (1 hour) \leq 7.8 mmol/L [140 mg/dL]

A dichotomous (responder / non-responder) endpoint will be defined based on whether a subject has reached an overall mean 1 hour PPG \leq 7.8 mmol/L [140 mg/dL] 16 weeks after randomisation, where PPG is derived from the 7-9-7-point SMPG profile.

This responder endpoint will be analysed based on a logistic regression model using treatment, region and metformin use at baseline (Yes/No) as factors, and baseline overall 1-hour mean PPG as covariate. In analysis of the in-trial observation period subjects without an overall mean 1 hour PPG at week 16 will be treated as non-responder. In the on-treatment observation period analysis subjects who discontinue randomised treatment, initiate ancillary treatment, withdraw from trial, or have no 1-hour mean PPG measurement at week 16 will be included as non-responders.

Overall PPG (1-hour) ≤7.8 mmol/L [140 mg/dL] without severe hypoglycaemia

A dichotomous (responder / non-responder) endpoint will be defined based on whether a subject has reached an overall 1-hour PPG ≤7.8 mmol/L [140 mg/dL] 16 weeks after randomisation without any treatment emergent severe hypoglycaemic episodes.

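### The before-breakfast minus bedtime glucose endpoint uses one night per profile although two are recorded; averaging both is a cheap gain in precision whose size depends on an unstated correlation

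*SAP*

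**What the plan says.** Protocol v4.0 section 8.3.3 has subjects "perform a 7-9-7 point profile on the 3 consecutive days just before selected visits", and section 8.6.3 names these as Visits 14, 22 and 30, plus 30A. Table 8-2 sets out the three days: 7 points on Day -3, 9 points on Day -2 and 7 points on Day -1. The 4 am reading is scheduled for the Day -2 night only. The footnote to the table says that the last reading of the 9-point profile is also the first reading of Day -1.

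SAP section 2.4.2.1 uses the entire 7-9-7 profile for its derived endpoints, "except for the analyses of nocturnal endpoints where information in the 9-point SMPG profile will be utilised". Protocol v4.0 section 17.4.2.1 is worded the same way. The SAP then defines three nocturnal differences: 4 am minus bedtime, "before breakfast PG value minus at bedtime PG value", and before breakfast minus 4 am. Each is analysed as a change from baseline, "using a model similar to 1) except with the corresponding baseline values as covariate", where 1) is the multiple-imputation model of the primary analysis.

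For meal increments from the same profiles, the SAP averages over the days: "The mean of the derived increments will then be calculated separately for each meal". It gives no reason for treating the bedtime-to-breakfast difference otherwise.

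**The concern.** The restriction to the 9-point night is unavoidable for the two differences that need a 4 am value. It is not needed for before breakfast minus bedtime, whose two readings are also scheduled on the preceding night of the same profile. A difference between two single capillary readings on one night is noisy, and the noise enters twice: in the baseline covariate, and in the week 8 and week 16 outcomes. A second night would reduce both at no extra burden to subjects.

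What is at stake is the precision of one supportive estimate, and the amount of imputation when a reading on the 9-point night is missed.

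**Working it through.** **Which nights are recorded (Protocol Table 8-2)**

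| Night | Bedtime | 4 am | Next before-breakfast |
|---|---|---|---|
| Day -3 to Day -2 | yes (7-point day) | no | yes (first point of the 9-point day) |
| Day -2 to Day -1 | yes (9-point day) | yes | yes (last point of the 9-point profile) |

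Two nights are complete for before breakfast minus bedtime, and one for the 4 am differences. The SAP uses the second row for all three.

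**No figure in the plan to reproduce.** SAP section 2.1 covers only the four steps of the testing hierarchy. Neither document gives a standard deviation, a night-to-night correlation or a precision for any nocturnal endpoint. The size below therefore rests on assumptions and is shown as a range.

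**Without baseline adjustment.** Let r be the correlation between the two nights of one profile (assumed), with equal variance on both. The variance of the two-night mean relative to one night is v = (1 + r)/2, and the standard error falls by 1 − √v.

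| r | v | √v | Fall in SE |
|---|---|---|---|
| 0 | 0.50 | 0.707 | 29.3% |
| 0.2 | 0.60 | 0.775 | 22.5% |
| 0.4 | 0.70 | 0.837 | 16.3% |
| 0.6 | 0.80 | 0.894 | 10.6% |
| 0.8 | 0.90 | 0.949 | 5.1% |
| 1 | 1.00 | 1.000 | 0% |

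**With the endpoint's own baseline as covariate, complete data.** Let b be the correlation between nights at different visits (assumed, b ≤ r). The residual variance is 1 − b² with one night and v − b²/v with two. The ratio of standard errors is √[(v − b²/v)/(1 − b²)].

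- r = 0.2: the fall is 22.5% at b = 0. At b = 0.2 the ratio is √[(0.60 − 0.04/0.60)/0.96] = 0.745, a fall of 25.5%.
- r = 0.4: the fall is 16.3% at b = 0. At b = 0.4 the ratio is √[(0.70 − 0.16/0.70)/0.84] = 0.749, a fall of 25.1%.
- r = 0.6: the fall is 10.6% at b = 0. At b = 0.6 the ratio is √[(0.80 − 0.36/0.80)/0.64] = 0.740, a fall of 26.0%.

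For r between 0.2 and 0.6 the adjusted range is therefore about 11% to 26%. It reaches higher than the unadjusted range because averaging also removes error from the covariate.

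**Unequal variances.** If the added night has k times the standard deviation of the 9-point night, the simple mean still has the smaller unadjusted variance when (1 + k² + 2rk)/4 < 1, that is, when k < −r + √(r² + 3). This limit is 1.54 at r = 0.2 and 1.23 at r = 0.6. The added night would have to be 23% to 54% more variable before averaging did harm, and nothing in the documents suggests that it is.

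**The case against.** The strongest objection is that one common night makes the three differences an exact decomposition: (4 am − bedtime) + (breakfast − 4 am) = (breakfast − bedtime). Using a two-night mean for the total and one night for the parts breaks this. That is a real cost, although the SAP does not give it as a reason. It is small, because each difference is modelled separately with its own baseline covariate, so the adjusted treatment estimates need not add up under the current plan either. The same-night version can still be shown descriptively.

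Three further points have some force:

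- The exception clause does not say that only the 9-point profile is used. One night is still the natural reading, and if both were intended the text does not say how to combine them.
- The two nights differ in whether the subject takes a 4 am reading. The schedule is the same in both arms of a double-blind trial.
- The protocol carries the same rule, so the change has to be documented as a departure from it.

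A reader might also infer more than the documents support:

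- **A fixed loss of precision.** The plan supplies no correlation, so no single figure can be stated as fact.
- **Subjects dropping out of the analysis after a missed reading.** The model imputes missing values, so subjects stay in. The gain is less imputation, and it cannot be quantified from the documents.
- **A third usable night from the daily readings.** Subjects do "perform 4-point profiles every day from Visit 2 to Visit 30 for titration purposes", but Protocol section 8.6.3 reserves selected titration data for titration surveillance and keeps them out of the trial report. Only the two nights inside the 7-9-7 profile are clearly available.

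**Conclusion.** The point holds as a cheap improvement. Before breakfast minus bedtime is restricted to the single 9-point night although each 7-9-7 profile schedules two complete nights for it, and the SAP averages over days for comparable meal increments. The direction of the gain is certain for any night-to-night correlation below 1 with equal variances. Its size is conditional: about 23% to 11% off the unadjusted standard error for an assumed correlation of 0.2 to 0.6, and about 11% to 26% with the baseline covariate under the further assumption b ≤ r.

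The endpoint is supportive, outside the four-step hierarchy and not part of the power calculation. A reader might infer that the trial's conclusions are weakened. They are not: type I error, the primary result and the confirmatory claims are untouched, and using one night introduces no bias between the arms.

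**What to change.** In SAP section 2.4.2.1, define before breakfast minus bedtime at each visit as the mean over the two nights recorded in the 7-9-7 profile (Day -3 to Day -2 and Day -2 to Day -1), or as the single available night if one is incomplete. Apply the same definition at baseline. Keep the 9-point night for the two differences that involve 4 am. Report the same-night version of before breakfast minus bedtime descriptively, so that the decomposition of the night can still be read.

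The cost is a sentence or two in section 2.4.2.1, and an entry in SAP section 3, since SAP section 1.2 requires changes to the planned analyses to be described there and reported in the clinical trial report. The change should be made before database lock. It needs no new data and adds no burden to subjects. The downsides are that the added night has no 4 am reading, equally in both arms, and that the three modelled differences no longer share one night.
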